4.2. Secondary Objectives

The secondary objectives of this study are:

- To evaluate the safety and toxicity profile of LY3022855, as assessed by the Common Terminology Criteria for Adverse Events, version 4.0 (CTCAE v4.0)
- To assess the pharmacokinetic (PK) serum concentrations of LY3022855
- To document antitumor activity, per Response Evaluation Criteria in Solid Tumors, version 1.1 (RECIST 1.1) (Eisenhauer et al. 2009) and immune-related RECIST (irRECIST) (Wolchok et al. 2009) (Note: If a patient has confirmed progressive disease per RECIST 1.1 but not per irRECIST, the patient will be considered to have not progressed.)
- To assess the development of antibodies against LY3022855 (immunogenicity), as assessed by a validated immunogenicity assay

4.3. Exploratory Objectives

The exploratory objectives of this study are:

- To explore serum biomarkers that may be relevant to the mechanism of action of IMC-CS4, CCI
- To explore the pharmacodynamic effects of IMC-CS4 on tissue biomarkers, using flash-frozen baseline and posttreatment tumor biopsies
- To assess antitumor activity in bone, per the Prostate Cancer Clinical Trials Working Group (PCWG2) (Scher et al. 2008) criteria

5. Study Design

[figure not shown]
5.1. Summary of Study Design

Study I5F-MC-JSCB (JSCB) is a single-center, open-label, nonrandomized, noncontrolled Phase 1 study of intravenous (IV) LY3022855 in patients with advanced, refractory breast or prostate cancer. Eligible patients will receive LY3022855 as an infusion. Study JSCB is intended to explore clinical response and immunological activity of single-agent LY3022855 in approximately 40 patients (enrolled, of whom 36 will be evaluable), by assessment of biomarkers, cytokines, and immune cells. The study schema is shown in [Figure JSCB.5.1](#).

Patients with prostate cancer

Patients with breast cancer

*Additional patients may be enrolled if marked antitumor activity is demonstrated at this dose.

Abbreviations: LY = LY3022855 (IMC-CS4); PD = progressive disease.

Figure JSCB.5.1. Study design for I5F-MC-JSCB.

5.2. Determination of Sample Size

For this study, approximately 40 patients will be enrolled. Patients with prostate cancer will be treated at 1 of 2 dosages of LY3022855, and patients with breast cancer will be treated at 1 of 4 dosages of LY3022855. Of those enrolled patients, approximately 36 patients will be evaluable: 30 patients with advanced, refractory breast cancer and 6 patients with advanced, refractory prostate cancer.

CSF-1 is the primary pharmacodynamic biomarker documented in Study JSCA. Serum CSF-1 was quantified for 17 patients over time; that is, at baseline and 8 hours after the first infusion. All those patients had increased levels of CSF-1 at 8 hours, compared with the baseline level.

The effect size (or Cohen's d) is 5.81. Consequently, the power of observing any change between the eighth hour and baseline is close to 1 as long as the number of samples is ≥ 3 . However, when the effect size is as small as 1 for the pharmacodynamic markers other than CSF-1, the power is approximately 0.159 if only 3 patients are sampled.

For Dosages C and D (patients with breast cancer), the sample size of 10 for each dosage provides a reasonable power to explore preliminary signals of efficacy. Assuming that a true best overall response rate (ORR) less than 20% indicates inadequate antitumor activity, then at a one-sided type 1 error rate of 5%, the total sample size of 10 will provide 80% power if the true best ORR is 60% or higher, using a 2-stage design method as follows during the first stage, 5 patients will be enrolled and treated on each of Dosages C and D. If 2 or more of the 5 patients on either dosage (C or D) are observed to be responders by the end of the first stage, an additional 5 patients will be enrolled at the applicable dosage. Then, if 5 or more of the total of 10 patients at that dosage are observed to be responders by the end of the second stage, further exploration of drug efficacy is warranted for that dosage.

6. A Priori Statistical Methods

6.1. General Considerations

Statistical analysis of this study will be the responsibility of the sponsor. The analyses for this study will be descriptive, except for exploratory analyses of biomarker data, as deemed appropriate. Analyses of the biomarker data will be described in a separate biomarker SAP.

Data analyses will be provided by cancer type, dose group, and for all study patients combined, wherever appropriate. For continuous variables, summary statistics will include number of patients, mean, median, standard deviation, minimum, and maximum. Categorical endpoints will be summarized using number of patients, frequency, and percentages.

The following data handling conventions will be used in the analysis (see [Table 6.1](#)).

Table 6.1. Data Handling Conventions

Term	Definition or Rule
Relative Study Day	If assessment is on or after date of first dose then (date of assessment) – (date of first study drug dose) +1
	If assessment precedes first dose of drug then (date of assessment) – (date of first study drug dose)
	There is no study day 0. Study day 1 is the date of first dose and study day -1 is the day before the first dose.
Baseline	For change from baseline analyses, baseline value is defined as the last reported measure on or before the first dose date (prior to the dose administration), unless, otherwise, specified. For change from baseline within a cycle, baseline value is defined as the measure prior to the first dose of that cycle, unless, otherwise, specified.
Entered	Patients who have signed the informed consent document directly.
Enrolled population	Patients who have been assigned to study treatment and have received at least 1 dose of any study treatment.
Screen Failures	Patients who have signed informed consent, do not meet eligibility criteria and are not enrolled.
Evaluable population	Patients who complete 1 cycle of LY3022855 treatment, undergo 1 baseline and 1 posttreatment tumor biopsy procedure, and complete immune blood studies for 1 cycle
Safety Population	Patients who have received at least 1 dose of study drug.

6.2. Handling of Dropouts or Missing Data

Missing data will not be imputed.

6.3. Patient Disposition

A detailed description of patient disposition will be provided. It will include a summary of the number and percentage of patients entered into the study, enrolled in the study, reasons for discontinuation from study treatment, and reasons for discontinuation from study. Reason for

discontinuation from both study treatment and the study will be listed by the pre-determined categories. All patients entered in the study will be included in the summary.

All clinically relevant protocol deviations will be listed by pre-determined categories (for example, inclusion/exclusion criteria, noncompliance with protocol procedures, drug dosage/intervention, use of excluded treatments, informed consent/assent process, continuing after meeting withdrawal criteria, or other).

6.4. Patient Characteristics

6.4.1. Demographics and Baseline Disease Characteristics

Patient demographics and baseline disease characteristics will be listed for all patients on therapy and summarized by cancer type, dose group, and overall.

Patient demographics will include sex, race, age, height, weight, and body mass index (BMI). Baseline disease characteristics will include initial pathological diagnosis and Eastern Cooperative Oncology Group (ECOG) performance status.

6.4.2. Historical Illnesses

Historical illnesses are clinically relevant events in the past that ended before the screening visit. Historical illnesses (using Preferred Term(s) [PTs] from the most current version of the Medical Dictionary for Regulatory Activities [MedDRA]) will be listed for all patients on therapy.

6.4.3. Prior and Post Discontinuation Therapies

Prior systemic therapy, radiotherapy, and surgeries will be listed and summarized for all patients on therapy. Any posttreatment therapies occurring during the study follow up period will also be listed.

6.5. Concomitant Therapy

All medications will be coded to the generic preferred name according to the current World Health Organization (WHO) drug dictionary. All concomitant medications will be listed and summarized using the preferred name for all patients on therapy by cohort. If concomitant medication use is due to an AE, the associated National Cancer Institute's (NCI) CTCAE v4.0 (NCI 2009) term will be listed.

6.6. Efficacy Analyses

One of the secondary objectives of the study is to measure any antitumor activity. Thus, tumor response data will be reported using listings and descriptive statistics. The ORR is estimated by the proportion of enrolled patients who have a best overall response of complete response (CR) or partial response (PR). The disease control rate (DCR) is estimated by the proportion of enrolled patients who have a best overall response of CR, PR, or stable disease. A 95% exact confidence interval will be constructed to determine the level of precision of the ORR and DCR, if appropriate. Time-to-event variables such as progression-free survival (PFS), duration of response, and overall survival (OS) will be tabulated, if appropriate. The Kaplan-Meier method

(Kaplan and Meier 1958) will be used to estimate the survival curves, medians, and survival rates at specified time points, if applicable.

6.7. Pharmacokinetic/Pharmacodynamic Analyses

Pharmacokinetic analyses will be conducted on patients who have received at least 1 dose of the study drug and have had samples collected, and PK serum concentrations of IMC-CS4 will be determined.

The parameters for PK analysis will include, but not be limited to, maximum concentration (C_{max}) and trough concentration of LY3022855. Additional analyses will be performed, if warranted by data, and other validated PK software programs (for example, NONMEM) may be used, if appropriate and approved by Global Pharmacokinetic Management.

Pharmacodynamic data from all patients undergoing pharmacodynamic assessments will be analyzed.

A separate statistical analysis plan will be prepared for analyses of PK and pharmacodynamics data.

6.8. Biomarker Analyses

Biomarker analyses related to the exploratory objectives of this study will be described in a separate SAP, if deemed necessary.

6.9. Safety Analyses

6.9.1. Extent of Exposure

The number of cycles of treatment received, dose delays, and dose intensity will be summarized. Dose intensity will be defined as the percentage of the planned cumulative dose (based on treatment assignment) administered during the cycle. Dose adjustments including the reasons for dose adjustment will also be listed and summarized.

6.9.2. Adverse Events

All patients who receive at least 1 dose of any study drug will be evaluated for safety and toxicity. Adverse event terms and severity grades will be assigned by the investigator using CTCAE, v4.0. In addition, AE verbatim text will also be mapped by the sponsor or designee to corresponding terminology within MedDRA. Adverse events will be reported using a unified CTCAE/MedDRA reporting process:

- The CTCAE v4.0 term reported by the investigator will be mapped to the MedDRA PT and system organ class (SOC) of the corresponding MedDRA lowest level term (LLT), unless the reported CTCAE term is “Other – specify”
- If the reported CTCAE term is “Other – specify” the MedDRA LLT, PT, and SOC mapped from the verbatim AE term will be used
- All listings and summaries will use the PT resulting from this process

A treatment-emergent adverse event (TEAE) is defined as any AE that begins on or after the day of the first dose of study drug or any preexisting condition that increases in CTCAE grade on or after the day of the first dose of study drug. Comparisons of preexisting conditions to on-treatment events at the LLT level will be used in the treatment-emergent computation.

The number of patients who experienced a TEAE, serious adverse event (SAE), or TEAE possibly related to study drug will be summarized. TEAEs will be summarized by SOC, by PT terms of decreasing frequency within SOC, and by maximum CTCAE grade and grade categories. Immune-related AEs may be tabulated, if deemed appropriate.

Historical illnesses are defined as events that ended before completion of the screening visit.

Preexisting conditions are defined as AEs that begin but do not resolve prior to the administration of the first dose of study drug. The preexisting conditions will be presented by patient and can be combined with the AE listing, so that the history of the preexisting conditions/AEs can be traced. Historical illnesses and preexisting conditions will be summarized and listed by dosage and overall for all patients on therapy if deemed appropriate.

6.9.3. Deaths

All deaths on study will be listed along with the reason for death, if known. A summary of deaths will also be produced.

6.9.4. Clinical Laboratory Evaluation

Laboratory data will be listed for all patients on therapy. Abnormal results will be listed separately for all patients on therapy. In addition to the investigator-reported AEs, all relevant hematology and chemistry laboratory values will be graded according to CTCAE v4.0. These calculated grades will be included on the listing and summarized by maximum postbaseline grade over the entire study.

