#### **5.4.5. Clinical Experience**

Clinical experience with LY3022855 comprises 43 patients (as of 28 January 2016) who received the following doses I.V. in 2 ongoing Lilly-sponsored Phase 1 studies (I5F-IE-JSCA [JSCA] and I5F-MC-JSCB [JSCB]): 2.5 mg/kg QW (n=6), 0.3 mg/kg QW (n=4), 0.6 mg/kg QW (n=3), 1.25 mg/kg Q2W (n=20), 1.25 mg/kg QW (n=5), and 1 mg/kg on Weeks 1, 2, 4, and 5 of every 6-week cycle (n=5). At the first human dose studied, 2.5 mg/kg QW (Study JSCA), which was also the highest dose administered, laboratory abnormalities, including Grade 2-3 creatine kinase (CK) and Grade 2-3 AST elevations, were noted in 5 patients but were not classified as dose-limiting toxicities (DLTs) due to the lack of clinical signs or symptoms of organ toxicity. Because of these laboratory abnormalities, the protocol for Study JSCA was amended and dose escalation was restarted at a lower dose, 0.3 mg/kg QW.

[figure not shown]
Elevated levels of CK and AST, in the absence of clinical signs or symptoms or other laboratory abnormalities suggestive of end-organ damage are, in retrospect, believed to be pharmacodynamic indicators of target engagement, rather than markers of drug-related toxicity. This belief is strengthened by findings of Radi et al. (2011), in which preclinical models support the hypothesis that increases in the levels of serum enzymes can be the result of decreases in Kupffer cells, in the apparent absence of hepatic or skeletal muscle injury. In all cases where elevated enzymes were observed following LY3022855 administration in Study JSCA, the levels decreased to Grade <2 upon discontinuation of LY3022855, indicating that these effects were reversible.

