#### 6.1.1. Inclusion Criteria

Patients may be included in the study if they meet all of the following criteria during screening prior to first dose of study drug.

- [1] Have a confirmed diagnosis of advanced, refractory breast or prostate cancer that is evaluable by radiologic testing. Patients must have experienced tumor progression on or treatment intolerance to at least one prior therapy for their cancer and have declined or are ineligible for a standard treatment.
- [2a] For patients with metastatic castrate-resistant prostate cancer (CRPC) only:
  - a) must continue ongoing androgen deprivation therapy (gonadotropin-releasing hormone [GnRH] agonist or antagonist) with castrate levels of serum testosterone <50 ng/dL determined within 4 weeks prior to starting treatment;
  - b) if receiving an antiandrogen as part of first-line hormonal therapy, must have shown progression of disease off the antiandrogen prior to enrollment;
  - c) must be willing to continue androgen deprivation therapy while on study, if no prior orchiectomy;

- d) must meet at least 1 of the following 3 criteria for progressive metastatic disease, according to PCWG2 criteria:
  - i. a rise in prostate-specific antigen (minimal value 2 ng/mL;  $\geq 3$  consecutive rising values), or
  - ii.  $\geq 2$  new metastases on transaxial imaging or radionuclide bone scan, or
  - iii. soft tissue progression;
- e) replacement hormone therapy (including prednisone or equivalent up to 10 mg/day) initiated before study entry is permitted per Section 7.5.

[2b] For patients with breast cancer only:

- a) may continue ongoing antiestrogen therapy (for example, an aromatase inhibitor),
- b) replacement hormone therapy initiated before study entry is permitted per Section 7.5, and
- c) may continue ongoing trastuzumab therapy.

[3] Are  $\geq 18$  years of age.

[4] Have given written informed consent prior to any study-specific procedures.

[5] Have adequate organ and hematologic function, including:

- Hepatic: Bilirubin  $\leq 1.5 \times$  the upper limit of normal (ULN), and ALT and AST  $\leq 3.0 \times$  ULN. For patients with tumor involvement of the liver, AST and ALT  $\leq 5.0 \times$  ULN are acceptable. For patients with tumor involvement of the bone, alkaline phosphatase  $\leq 5.0 \times$  ULN is acceptable.
- Renal: Serum creatinine  $\leq 2.0 \times$  ULN.
- Absolute neutrophil count (ANC)  $\geq 1.0 \times 10^9/L$ .
- Hemoglobin  $\geq 9$  g/dL (5.58 mmol/L).

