## 10.4. Safety Analyses

All patients who receive at least one dose of LY3022855 will be evaluated for safety and toxicity. Adverse event terms and severity grades will be assigned by the investigator using CTCAE v4.0.

All safety summaries and analyses will be based upon the Safety Population, defined as all enrolled patients who have received at least one dose of study drug.

Overall exposure to study drug, the numbers of patients completing each cycle, and the dose intensity will be summarized using descriptive statistics.

An overall summary will be provided for AEs deemed by the investigator to be possibly related to study medication, and repeated for events regardless of study drug causality.

The number of evaluable patients who experienced a TEAE, an SAE, or an AE related to study drug, or who died or discontinued from the study due to an AE will be summarized.

Reasons for death will be summarized separately for on-therapy and within 30 days after last dose of study drug.

Laboratory results will be classified according to CTCAE v4.0. Laboratory results not corresponding to a CTCAE v4.0 grade will not be graded.

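### The laboratory summary shows maximum postbaseline CTCAE grade with no baseline grade beside it, so an unchanged entry abnormality cannot be told apart from worsening

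*SAP*

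**What the plan says.** SAP 6.9.4 (Clinical Laboratory Evaluation) has two parts. First, "Laboratory data will be listed for all patients on therapy", with abnormal results listed separately. Second, "In addition to the investigator-reported AEs, all relevant hematology and chemistry laboratory values will be graded according to CTCAE v4.0", and then: "These calculated grades will be included on the listing and summarized by maximum postbaseline grade over the entire study". Nothing in the section refers to the grade before the first dose. Protocol 10.4 adds no baseline comparison; it says only "Laboratory results will be classified according to CTCAE v4.0".

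The SAP has the pieces that a comparison would need. Table 6.1 in SAP 6.1 says that, for change-from-baseline analyses, the "baseline value is defined as the last reported measure on or before the first dose date". SAP 6.9.2 applies a baseline rule to adverse events: a condition already present counts as treatment-emergent only if it is "any preexisting condition that increases in CTCAE grade on or after the day of the first dose of study drug". Section 6.9.4 uses neither.

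Protocol 6.1.1, criterion [5], allows AST and ALT up to 3.0 × ULN. It relaxes this as follows: "For patients with tumor involvement of the liver, AST and ALT" are acceptable up to 5.0 × ULN. It also allows:
- alkaline phosphatase up to 5.0 × ULN with bone involvement;
- bilirubin up to 1.5 × ULN and creatinine up to 2.0 × ULN;
- neutrophils from 1.0 × 10^9/L, hemoglobin from 9 g/dL and platelets from 90 × 10^9/L.

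CK has no entry limit.

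**The concern.** A table of worst postbaseline grade is easily read as a table of what happened on treatment. Here some patients are expected to arrive with abnormal values, often because of liver or bone metastases. A patient whose AST is raised at entry and never moves occupies the same cell as a patient whose AST rose from normal to that grade. The summary does not separate the two.

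This matters more here than in many trials, for two reasons. Enzyme elevation is the drug's prominent laboratory signal: Protocol 5.4.5 reports that, at the first dose level of the earlier study (6 patients), "Grade 2-3 creatine kinase (CK) and Grade 2-3 AST elevations, were noted in 5 patients", and dose escalation was restarted lower as a result. The trial is also nonrandomized and noncontrolled, so no concurrent group shows the background rate of abnormal values. SAP 6.1 plans summaries by cancer type and dose group. Among the first 5 patients on Dosage C or D, one patient is 1/5 = 20 percentage points of a row.

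**Working it through.** The plan states no figure on this point, so there is none to reproduce. The check is a comparison of sections, followed by an illustration on assumed rates.

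**1. Can an abnormal grade be present at entry?** The entry limits above allow values outside the normal range. The documents do not reproduce the CTCAE cut-offs, so the grade that a given entry value carries cannot be read from them. Three places in the protocol nevertheless show that abnormality at entry is expected:
- Attachment 1 requires preexisting toxicity to be graded by CTCAE v4.0 at baseline.
- Section 7.2.1 accepts a return to baseline as an alternative to Grade <2.
- Section 8.1.4 has a baseline-relative ALT trigger for patients who enter at or above 3 × ULN.

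**2. How does each safety output treat a stable entry abnormality?**

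| Output | Rule | Stable entry abnormality |
|---|---|---|
| TEAE tables (SAP 6.9.2) | Counted only if the grade increases | Not counted |
| Laboratory listings (SAP 6.9.4) | All values shown by patient | Visible with its baseline value |
| Laboratory grade summary (SAP 6.9.4) | Maximum postbaseline grade | Shown at its grade, as if new |

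Only the third output loses the distinction.

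**3. Illustration of the mechanism (assumed rates, not an estimate).** For one analyte, let b be the share entering at Grade 1 or higher and remaining abnormal. Let w be the share whose grade truly rises, taken as independent of b. Then:

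- share shown with any postbaseline grade = 1 − (1 − b)(1 − w)
- excess over true worsening = b(1 − w)

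With the 40 planned patients:

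| b | Shown if w = 0 | Shown if w = 10% |
|---|---|---|
| 10% | 4 | 7.6 |
| 20% | 8 | 11.2 |
| 30% | 12 | 14.8 |
| 50% | 20 | 22 |

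For example, with b = 20% and w = 10%: 40 × (1 − 0.8 × 0.9) = 11.2 shown, against 40 × 0.10 = 4 who worsened. A count of grade increases would show 0 in the first column and 4 in the second, whatever the value of b.

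Over b from 10% to 50% and w from 0 to 30%, the excess runs from 40 × 0.10 × 0.70 = 2.8 to 40 × 0.50 × 1 = 20 patients. A range that wide shows that the size depends almost entirely on baseline rates the documents do not give. It also assumes that every entry abnormality counted in b persists.

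**The case against.** The best defence is that the table is accurate for what it claims to be. SAP 6.9.4 does not call these grades toxicity, treatment-emergent or drug-related. It describes calculated grades, reported in addition to adverse events. A reader might infer that the plan counts entry abnormalities as on-treatment drug toxicity. The documents do not support that reading, and this part of the defence stands.

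Several further limits also stand:
- Protocol 8.1.2 requires clinically significant laboratory findings to be reported as adverse events, and these then pass the grade-increase rule in SAP 6.9.2.
- Baseline values remain in the listings, and with groups this small a reader can trace each patient.
- No decision rule cites this summary. Expansion of Dosages C and D turns on responder counts, so an inference that it distorts a go/no-go decision has no basis in the text.
- AST, ALT and CK are also sampled as pharmacodynamic or isoenzyme measures, and SAP 6.7 sends pharmacodynamic data to a separate plan that is not among these documents. That plan may report change from baseline.
- Where criterion [5] caps an analyte, the excess probably lies mainly in the lower grades, whereas the earlier study's signal was Grade 2-3. CK has no cap, so this reassurance does not extend to it.

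None of this restores the missing comparison in the summary. A listing allows reconstruction patient by patient; it does not correct the table that readers will use first.

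**Conclusion.** The point holds as a limitation of one descriptive summary. SAP 6.9.4 states a definite rule that ignores baseline grade, in an uncontrolled trial whose entry criteria admit abnormal values, and it departs from the SAP's own approach to adverse events. An unchanged entry abnormality will appear there as a postbaseline grade.

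Its size is unknown. The conclusion that some patients are affected assumes that some permitted entry values carry a non-zero CTCAE grade and persist. The patient counts in the illustration show how the mechanism works and should not be quoted as expected numbers. Nor do the documents show that the effect differs between dosages. It is a worthwhile, inexpensive improvement and does not threaten the trial's conclusions.

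**What to change.** In SAP 6.9.4, add for each graded analyte a shift table of baseline grade (Table 6.1 definition) by worst postbaseline grade, presented by dosage and cancer type. Add a count of patients whose worst postbaseline grade exceeds their baseline grade. Keep the maximum postbaseline grade as the margin of the shift table, so that the planned counts are preserved, and keep the listings as they are.

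The cost is a short change to the SAP text and one standard table. Attachment 1 already schedules hematology and chemistry within 14 days before Day 1 and on Day 1, and Attachment 2 includes CK in the chemistry panel. No new samples, visits or data fields are needed.

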Based on these observations, the protocol for Study JSCA was amended to: (1) examine fixed (non-weight-based) dosing of LY3022855 on weekly administration schedules to optimize the biological effects of LY3022855 on CSF-1R inhibition, (2) redefine a DLT as any LY3022855-related AE that occurs during Cycle 1 and does not improve to Grade  $\leq 2$ , unless stated otherwise, despite medical management, including steroids (if applicable) within 7 days of documented occurrence, and (3) incorporate management guidelines for immune-related AEs. Dosing in Study JSCA resumed at a fixed dose of 100 mg QW, which is comparable to 1.33 mg/kg in a 75-kg person and within the coefficient of variation in exposure (34% to 49%). As of 12 October 2016, 3 patients in Study JSCA have received 100 mg QW for 6 weeks (Cycle 1, DLT assessment period) without experiencing a DLT. Of the 3 patients treated at the next higher dose level of 150 mg QW, 1 patient experienced a DLT of Grade 3 CK elevation associated with elevated serum and urine myoglobin.

Abbreviation: C = cohort.

**Figure JSCB.2.      CD14dimCD16bright (relative percentage of CD45+ HLA-DR+ CD14+) in the blood of patients from Study JSCA.**

More information about the known and expected benefits, risks, and reasonably anticipated AEs may be found in the IB. Information on AEs expected to be related to the investigational product may be found in Section 7 (Development Core Safety Information) of the IB. Information on SAEs expected in the study population independent of drug exposure and that will be assessed by the sponsor in aggregate, periodically during the course of the study, may be found in Section 6 (Effects in Humans) of the IB.

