#### **Additional tests to be performed, as clinically indicated, at a routine follow-up visita**

- Serum myoglobin – if CK  $\geq 2.5 \times$  ULN
- Urine myoglobin – if CK  $\geq 2.5 \times$  ULN

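### SAP 6.9.4 plans no laboratory summary pairing CK with myoglobin or AST/ALT with bilirubin, although the protocol uses those pairings to separate presumed target engagement from injury

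*SAP*

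**What the plan says.** SAP 6.9.4 specifies three laboratory outputs.

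- Listings: "Laboratory data will be listed for all patients on therapy. Abnormal results will be listed separately for all patients on therapy".
- Grading: "all relevant hematology and chemistry laboratory values will be graded according to CTCAE v4.0".
- Summary: the grades are "These calculated grades will be included on the listing and summarized by maximum postbaseline grade over the entire study".

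Protocol 10.4 (Safety Analyses) adds that "Laboratory results not corresponding to a CTCAE v4.0 grade will not be graded". Neither document names a table that combines two analytes.

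The protocol reads these enzymes in combination in several places.

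- **5.4.5, Clinical Experience.** CK and AST rises without clinical signs, symptoms or other laboratory evidence of organ damage are "believed to be pharmacodynamic indicators of target engagement, rather than markers of drug-related toxicity". In the parent study at 150 mg QW, by contrast, "1 patient experienced a DLT of Grade 3 CK elevation associated with elevated serum and urine myoglobin".
- **Table JSCB.3 and Attachment 10.** How a CK rise is handled depends, among other things, on whether serum and urine myoglobin are raised. Attachment 10 likewise treats an AST or ALT rise differently according to total bilirubin.
- **6.3.1, Discontinuation of Patients.** One criterion requires AST or ALT of Grade 2 or more together with bilirubin of Grade 2 or more.
- **8.1.4, Safety Monitoring.** One trigger requires ALT of at least 5 × ULN together with total bilirubin of at least 2 × ULN.

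Attachment 2 does not list myoglobin under hematology or clinical chemistry. It appears under the heading "Additional tests to be performed, as clinically indicated, at a routine follow-up visit" and is triggered by CK of at least 2.5 × ULN.

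**The concern.** CTCAE grades one laboratory test at a time, so the natural reading of SAP 6.9.4 is a table of worst grade per analyte, although the SAP does not say so in those words. Such a table drops the two features on which the protocol's distinction rests: whether a second analyte was abnormal in the same patient, and whether the two were abnormal at the same time.

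Safety is a secondary objective, and protocol 8.1.4 names hepatotoxicity and muscle damage for review. If the drug commonly raises CK and AST through its mechanism, the maximum-grade table will mainly count that effect. A few cases of true muscle or liver injury would sit in the same cells without being marked. A reader comparing Dosages A to D on that table could not tell which kind of rise a dosage produced.

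**Working it through.** The plan states no figure for this point, so there is none to reproduce. The check has three parts.

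**1. Does grade alone discriminate in the protocol's own data?** Protocol 5.4.5 reports two parent-study observations.

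- At 2.5 mg/kg QW, 5 patients had Grade 2-3 CK and AST elevations that were not classed as DLTs.
- At 150 mg QW, 1 of 3 patients had a DLT of Grade 3 CK with raised serum and urine myoglobin.

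The first grade range includes the grade of the second case. A Grade 3 CK rise enters the same cell of a maximum-grade table in either situation, so grade alone does not separate them.

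**2. What do separate counts say about a combined event?** Let n be the patients in a cohort, a the number with a high maximum grade on one analyte, and b the number on the other. The number with both at any time lies between max(0, a + b − n) and min(a, b). The plan gives no a or b, so the values below are assumptions shown over a range. The size n = 10 is the full size of Dosage C or D, and n = 40 is the approximate total enrolment.

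| n | a | b | a + b − n | Patients with both: lower | Upper |
|---|---|---|---|---|---|
| 10 | 3 | 1 | −6 | 0 | 1 |
| 10 | 3 | 2 | −5 | 0 | 2 |
| 10 | 5 | 3 | −2 | 0 | 3 |
| 40 | 8 | 4 | −28 | 0 | 4 |
| 40 | 12 | 6 | −22 | 0 | 6 |

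In every case shown the table is compatible with no combined case and with the largest possible number. These bounds are for both abnormalities at any time during the study. The number with both in the same sample cannot exceed the same upper limit, and its lower limit is 0.

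For CK and myoglobin the position is weaker still. Myoglobin is outside the hematology and chemistry lists, so the planned table supplies a but may supply no b. The joint count is then known only to lie between 0 and a. This does not depend on whether CTCAE has a myoglobin grade, which the documents do not settle.

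**3. Do other planned outputs give the paired count?**

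- SAP 6.9.2 summarises TEAEs by preferred term and maximum grade, again one term at a time. A laboratory finding enters only if it is reported as an adverse event; protocol 8.1.2 requires this for clinically significant findings.
- The immune-related adverse event table in SAP 6.9.2 is optional.
- Reasons for dose adjustment (SAP 6.9.1) and for discontinuation (SAP 6.3) are summarised, but no combined laboratory category is stated.
- The listings in SAP 6.9.4 do hold the values needed to rebuild the pairs by hand.

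No planned summary therefore yields the paired count, although the patient-level data do.

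**The case against.** The strongest case on the other side is that little is lost. SAP 6.9.4 lists every laboratory value and lists abnormal results separately. With about 40 patients, and 5 to 10 each on Dosages C and D, a reviewer can trace pairs patient by patient. Adverse event tables and reasons for dose change or stopping are further routes, and the combined hepatic criterion in protocol 6.3.1 is itself a reason to stop. The analysis is descriptive, the cohorts are not randomised, and expansion of Dosages C and D turns on responders, not on laboratory grades. The paired rules in the protocol also govern management and monitoring and do not define harm. Protocol 5.4.5 does not mention myoglobin when it describes target engagement, and Table JSCB.3 also requires the CK rise to be asymptomatic.

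Most of this stands as a limit on the point. A reader might infer that the study's output as a whole cannot distinguish injury from target engagement; the listings rule that out. Nor would a CK-by-myoglobin table settle the distinction alone, since symptoms also count.

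A reader might also set 5 of 6 patients (83%) with raised enzymes at 2.5 mg/kg QW against 1 of 3 (33%) at 150 mg QW and infer that a maximum-grade table would reverse the true ordering of harm. The documents do not support that, for four reasons.

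- The 1 of 3 is a DLT count. The number with raised enzymes at 150 mg QW is not given; were it 3 of 3, the comparison would be 100% against 83%.
- No myoglobin values are reported for the 5 patients.
- The DLT definition was amended between those cohorts.
- Neither dose is used in this study.

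Finally, separate maxima do not make two unrelated peaks look like one combined case. They leave co-occurrence unknown.

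The objection does not remove the gap. Reading listings without a stated definition or matching window is not a prespecified summary, and the other tables also work one term at a time or are optional.

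**Conclusion.** The point holds for the summary tables. The one planned laboratory summary is by maximum grade, and no planned table pairs CK with myoglobin or AST/ALT with bilirubin. The number of combined cases is therefore undetermined from the tables: from 0 up to the smaller of the two counts for transaminases and bilirubin, and from 0 up to the whole CK count where myoglobin is not summarised. The parent-study data show only that grade alone does not discriminate.

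This rests on reading the maximum as taken per analyte, and on taking the planned tables to be those the SAP names. The counts in the worked ranges are assumptions. The weakness is one of reporting, with no effect on a decision rule. It should be corrected because the protocol makes the distinction itself and the correction is cheap.

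**What to change.** Keep the maximum-grade table. Add to SAP 6.9.4, by dosage and overall:

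- **(a) CK grade by myoglobin status at the same episode**: serum and urine both above ULN, one above, neither above, or not measured. The SAP should state the window that counts as the same episode, because myoglobin is a triggered test and may follow the CK result. It should also state how a patient with several episodes is counted.
- **(b) Number of patients with AST/ALT and total bilirubin elevations in the same sample.** Report this once for the criterion in protocol 6.3.1 (CTCAE grades of AST or ALT with bilirubin) and once for the criterion in 8.1.4 (ULN multiples of ALT with bilirubin). Label each as the protocol writes it and do not merge them. No new clinical threshold is needed.

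Any plot of ALT against bilirubin should use same-sample values, or mark whether the two peaks coincide; otherwise it repeats the timing problem.

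The cost is SAP wording and two small tables. AST, ALT, total bilirubin and CK are in one chemistry panel, drawn weekly for the first 12 weeks, and myoglobin is already collected when triggered. The drawbacks are sparse counts and some cells for myoglobin not measured, which should be shown and not dropped.
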